Clinical Trial Protocol: MS HELLEN Trial

Title

A phase 1 pre-post intervention trial with 12 week baseline control determining the merits of a lower limb robotic exoskeleton (HELLEN) in the rehabilitation of Multiple Sclerosis (MS).

Title Registration

Registry: ANZCTR : to be confirmed upon ethics approval

Protocol Version

11th July 2017

Funding

A REX Bionics Exoskeleton has been provided in-kind to the research team by the Australian Institute of Neuro-rehabilitation (AIN). This is a not for profit organisation with an agenda to improve services to neurological patients in the community. The researchers have a working relationship with the AIN to facilitate this research.

Roles and Responsibilities

The research team includes [name], University of Newcastle (Chief Investigator); [name], HMRI (Chief investigator); Associate [name], University of Newcastle (Chief investigator); and [name], University of Newcastle (PhD student, and primary therapist conducting the assessments and providing the intervention).

Associate [name] and [name] are involved in the recruitment of patients via the database associated with the specialised MS clinic in Newcastle, MS Base, which has grown to be to one of the largest in the country with over 700 patients.

The data will be collected, managed and analysed by the research team. Submission of scientific papers for publication will involve the whole research team and will remain the intellectual property of the University of Newcastle.

Background and Rationale

Emphasis on training in the performance of functional activities, together with attempts to improve muscle strength and coordination, continue to form the central focus of most rehabilitation programs. However, for severely affected patients, task specific training for walking is labour intensive and puts a substantial physical burden on therapists who have to facilitate movement of the limbs whilst supporting the patient to prevent falls and guarantee safety (Schuck A, Labruyre R, 2012). Several therapists are required yet despite this, systematic correction of a patient's weight shift and stride length is often not possible. In daily practice, budget constraints limit intensive hand to

hand therapy regimes and the duration of therapy sessions is therefore restricted. Essentially access to therapy in a supported standing position for those severely impaired by neurological conditions, such as MS, is largely denied (Hess, Schmidt 2003). “There has been a recent surge in research examining the effect of exercise on functionality, and a corresponding interest in the impact of exercise on quality of life (QoL). A growing body of evidence suggests that substantial QoL benefits can be gained by MS patients who engage in exercise” (Horton et al, 2010). As those severely mobility impaired patients with MS have limited access to weight-bearing therapy, there is increasing interest in the use of robotic training devices to assist therapists as they provide opportunities to increase the intensity and dosage of training and reduce the physical demands and safety of therapists and patients (Freekotte, Koopman 2014).

It is the growing evidence detailing the importance of task specific training and active standing, in tandem with advances in engineering that has led to the development of robotic technology with the capacity to facilitate gait. These are wearable lower body exoskeleton orthosis with joints and limbs corresponding to those of the human body. Several devices are currently available, but The REX Robotic Exoskeleton is unique as it does not require the use of crutches to support the upper body meaning that the user has full use of his arms/hands to allow the performance of tasks independently in standing (REX Bionics, 2016). This is an important clinical distinction as patients with MS often have weakness in their upper limbs, and cannot always use walkers/crutches to stabilise their bodies effectively. The technology offers several advantages over conventional rehabilitation strategies, especially for individuals with severe motor impairments. REX is a self-supporting robotic device, independently controlled with a joystick and control pad allowing even severely impaired patients to use it. It gives people the ability to stand, get up, turn around, exercise in a weight-bearing standing position, and sit down again on their own. As such it has substantial clinical potential and opens new perspectives for weight bearing exercise and task specific mobility training in MS patients.

The Hunter has been very fortunate that collaboration with the Australian Institute of Neuro-rehabilitation (AIN) has procured the purchase of a REX exoskeleton (HELLEN: Hunter’s Exoskeleton for Lower Limb Exercises and Neuro-rehabilitation) and motor vehicle for transport, through a donation from the Newcastle Permanent Charitable Foundation. This is the first purchase of this robotic device in Australia.

There is, to date, no published clinical research evaluating the use of the REX Bionics exoskeleton in patients with MS. The vast majority of anecdotal evidence is also in relation to the use of the REX with spinal cord injured patients. Therefore, there is a need for independent research to establish the feasibility, acceptability and efficacy of lower limb robotics as a potential rehabilitation modality in the MS population.

We anticipate that this pilot study will provide the preliminary data required about safety, feasibility and effect size estimates, which is necessary for progression to a larger randomised trial, if warranted. The results of this trial will complement those from the clinical trial currently underway by this research team investigating the merit of this robotic exoskeleton in the Acquired Brain Injured population.

Objectives

The aim of this project is to examine the potential benefits and applicability of using HELLEN as an adjunct tool for neurorehabilitation in MS, as well as highlighting any barriers and risks to its potential use in this population. It is anticipated that this pilot data will assist in establishing priorities and directing further research in this field.

Trial Design

A phase 1 pre-post intervention trial with 12 week baseline control. This study design has the advantage of allowing all recruits in the study to receive the robotic exercise intervention. We aim to recruit 20 participants in this first stage pilot trial.

Study Setting

The trial will operate at one site only, at the University of Newcastle. A research room has been purpose built for this research in the Hunter Building with designated parking space for participants.

Eligibility Criteria

Inclusion Criteria:

1. Diagnosis of MS
2. Resident of the Hunter region over the age of 18 years
3. Severe mobility impairment whereby the participant is reliant on a mobility aid or other people for upright activities (Scores >6 on the Expanded Disability Status Scale)

Exclusion Criteria

1. Weight >100kg or <40kg; height >6'4" or <4'8" (criteria set by the REX Bionics)
2. Pregnancy
3. Unstable or severe cardiac or respiratory conditions
4. Recent fractures in lower limbs/pelvis/spine
5. Significant cognitive impairment (<19 on MoCA)
6. Any medical condition which limits the ability to exercise in an upright position

The treatment will only be delivered by REX trained Physiotherapists. Researchers, [name] and [name] have both completed the full 3 day training course and attained competency accreditation.

Intervention

The intervention will involve 2 sessions of exercise therapy per week for 12 weeks. Each session will be up to 1 hour duration and will consist of half an hour of individualised therapy, prescribed and administered by a physiotherapist, including upright weight-bearing exercise facilitated by HELLEN as tolerated by the patient. This may be a combination of sit to stand practise, standing tolerance, weight shift, trunk control exercises, stepping practise, side stepping, squats, upper limb exercises and gait practise. These exercises will be individually tailored to meet the abilities and needs of the client. Participants will also be provided with a home exercise program

relevant to their treatment, which will be assessed and updated throughout the trial as required.

Interventions will only be progressed according to the individual participants' abilities as deemed appropriate by the administering physiotherapist. Interventions will be modified or ceased if, in communication with the participant, the researchers deem that this is necessary.

Outcomes

The timepoints for assessment of outcome measures are:

Week 0: Assessment and assignment to waiting list

Week 12: Commencement of therapy phase

Week 18: Mid- therapy assessment phase

Week 24: End of therapy phase

Week 36: Follow-up phase, 12 weeks after completion of intervention

Participants will be screened for eligibility and baseline measurements will be taken before participants are assigned to a 12 week waitlist. The primary outcome of interest is functional ability as measured by the Motor Assessment Scale. Secondary outcomes include a range of impairment, mood, fitness, and quality of life measures as listed below:

All assessment forms are attached and include:

1. Medical screening form: to determine eligibility for exercise and suitability of the robotic device
2. Demographic information: Standard demographic and MS information including Kurtzke Expanded Disability Status Scale (EDSS)
3. Cognitive screen MoCA
4. Mood HADS
5. Attitude towards robotic therapy questionnaire
6. Routine physiotherapy assessments using standardised outcome tools: fatigue (FAS), function (MAS and sit to stand test), spasticity (Tardieu), quality of life (SF8), balance (functional reach), independence (Barthel Index), fitness (O2 consumption using the Cosmed K5) strength (dynamometer).
7. Those agreeing to exercise/O2 consumption testing will be assessed wearing the Cosmed K5 O2 mask. During their 3rd or 4th treatment session in HELLEN the participants will be assessed wearing the Cosmed K5 mask, during their 30 minute treatment session in HELLEN. This testing will be repeated during their final HELLEN treatment session.
8. Bioelectrical Impedance Analysis to assess changes in body composition.

Participant Timeline

Potential participants will be identified on the MS database by research nurse, [name]. She will then make telephone contact with potential participants to inform them

of the research and gauge their interest in participating. Those interested, will be provided with an information statement detailing the study and will be contacted by [name], in the following week by phone, to answer any questions they may have and if still interested, to arrange a convenient time for an assessment. Once they are deemed eligible, baseline measures will be collected and they will be placed on a 12 week waitlist. These measures will be repeated after the 12 week period, after 6 weeks of intervention, at the conclusion of 6 weeks of intervention and 12-weeks after the intervention period. After the wait period, twice weekly sessions will continue for 12 weeks. They will then be provided with an ongoing home exercise program. In total, participants will be enrolled in the study for 36 weeks.

Sample Size

20 participants with MS will be invited to participate in this pilot trial.

Recruitment

Potential participants will be identified by [name] via the database maintained by the Newcastle MS clinic, MS Base.

Data Collection Methods

Data will be collected by [name] in the Physiotherapy Robotics Laboratory (HE14) at the University of Newcastle. Outcome measures will be collected at the beginning of the waitlist phase, the commencement of the trial phase, 6 weeks into the intervention phase, at the end of the intervention (12 weeks), and at the 12 week follow up appointment. The outcome measures have been attached. They have been chosen to reflect a variety of expected benefits of the intervention, and the range of impairments experienced by people with MS.

As the intervention is at no cost to the participants, and offers a type of treatment not currently available to MS patients, there is inherent motivation for the participants to maintain their continued participation in the trial, until the completion of the follow up. For any participants who are lost to follow-up, their last measurements will be imputed into the data and analysed according to intention to treat principles.

Data Management

All data collected from individuals will be maintained in a de-identified form. The data records will be coded using alphanumeric coding to differentiate individual subjects for purposes of analysis. The key for the code will be stored separately on a password protected personal computer. This coding process will be final and subjects will not be re-identified unless they wish to be removed from the study in which case their data will be re-identified, removed from analysis, and destroyed.

Paper copies of clinical measures will contain identifying information about each participant – these will be kept in a separate locked filing cabinet, within the chief investigator's office. Identifying information (names, addresses and contact details)

will not be kept on any database or computer file from the creation of these data files. The data will be coded using an alphanumerical system and the code sheet will be kept in a password protected file on the researcher's computer. Databases will be kept on secured networks (accessible only via password to the researchers named on this application) and hard drive back-up copies will be kept in the same locked filing cabinet as the paper data.

Video files will be downloaded onto the researcher's password protected computer, and deleted from the camera.

All data and findings will be kept for 5 years, consistent with criteria for scientific fraud issues. After that time, all data will be disposed of by shredding or electronic deletion.

In the event that principle investigator [name] ceases to be engaged with the University of Newcastle, [name] will assume responsibility for the study data.

Statistics

The data collection phase of the trial is expected to take a year. Descriptive statistics, including means and standard deviations (SD), will be calculated for demographic and outcome data. Change scores for each outcome from baseline will be tested using independent t tests for continuous variables and χ^2 tests for categorical variables. Differences from enrolment, baseline, post intervention and 12-week follow up will be evaluated for statistical significance. All analyses will be conducted on an intention-to-treat basis, with missing follow-up data conservatively imputed using the last observation carried forward method. All statistical analysis will be conducted by a qualified statistician.

Descriptive statistics, including means and standard deviations, will be calculated for demographic data. A linear mixed model will be used to detect a significant difference between outcome scores during each time period. The value of the baseline score at the start of the trial and after intervention will be used as a covariate, and analysis conducted to correct for differences in baseline scores and to ensure there is no effect of order. All analyses will be conducted on an intention to treat basis, with missing follow-up data conservatively imputed using the last observation carried forward method.

Data Monitoring

This is a pilot study. No formal interim analysis or DMC is required.

This study will be internally monitored. Chief investigators [name], [name] and [name] will be responsible for ensuring treatment application, data collection, analysis and statistical evaluation are all conducted within accepted scientific practices. Patients will be monitored carefully during the administration of the treatment and adverse events will be documented and submitted to the HREC for evaluation.

Harms

Adverse events will be immediately reported to the ethics committee.

Research Ethics Approval

Application for ethics approval has been given by the Hunter New England Human Research Ethics Committee (17/08/16/4.02).

Protocol Amendments

Protocol amendments affecting future participants will be communicated via a revised participant information form. The research protocol, where necessary, will be revised and disseminated to all relevant parties.

Informed Consent

This will be obtained via the attached form, and completed upon initial contact with [name] – the researcher/physiotherapist responsible for providing the intervention.

Confidentiality

This will be maintained in accordance with routine therapist-patient requirements, and all data will be stored as previously outlined.

Declaration of Interests

All investigators work in the field of neurological therapy/medicine and/or research. Their interests outside of this clinical trial are aligned with the research. There are no conflicts of interest to declare.

Access to Data

All investigators ([name], [name], [name], and [name]) will be able to access the data for analysis, which will lead to the publication of manuscripts for submission to scientific journals.

Ancillary and post-trial care

Those who participate in the trial will be provided with an updated home exercise program on completion of the trial, and advice about local therapy services that may be relevant for ongoing rehabilitation or health care. If interested, the participants will be informed of future research activity by this research team.

Dissemination Policy

All participants will be provided with a summary of the findings from this research and will be offered the option of receiving a copy of any publications relating to this research.

There will be no professional writers employed. The scientific papers and conference presentations relating to the study will be generated by the research team.

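### Attitude to robotic therapy is first measured after exposure at week 18, and for participants lost before then the plan carries forward an answer given before they had used HELLEN

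*Protocol*

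**What the plan says.** The Background and Rationale says that independent research is needed to "establish the feasibility, acceptability and efficacy of lower limb robotics". Of the forms listed under Outcomes, item 5, "Attitude towards robotic therapy questionnaire", is the only one that bears directly on acceptability.

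The assessment times under Outcomes include "Week 12: Commencement of therapy phase" and then "Week 18: Mid- therapy assessment phase". Participant Timeline says of the baseline measures: "These measures will be repeated after the 12 week period, after 6 weeks of intervention". Data Collection Methods gives the same order: "Outcome measures will be collected at the beginning of the waitlist phase, the commencement of the trial phase, 6 weeks into the intervention phase". Only the oxygen consumption test has a timing of its own within therapy.

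The Intervention section foresees early stopping: "Interventions will be modified or ceased if, in communication with the participant", where the researchers judge it necessary. No assessment is tied to that event.

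On missing data, Data Collection Methods states: "For any participants who are lost to follow-up, their last measurements will be imputed into the data". The Statistics section applies LOCF to missing follow-up data in all analyses and describes it as conservative. Data Management adds a separate rule: participants who wish to be removed from the study have their data taken out of the analysis and destroyed.

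**The concern.** An attitude score from someone who has not yet used the device is an expectation. One from someone who has used it is an experience. Early leavers may include the people who found HELLEN hardest to accept. If they are lost before week 18, the trial holds only their expectation, and the stated rule enters it at visits meant to describe experience.

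For a functional score, LOCF can be defended as denying the intervention any gain that was not observed. For attitude the argument can reverse, because a possible rejection is replaced by an untested opinion. The Objectives ask the pilot to bring out barriers to use and to direct further research, so the missing view is one the trial has reason to want.

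This is first a gap in collection. A later analysis plan could drop the carried-forward value, but it could not supply an answer that nobody asked for.

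**Working it through.** The protocol gives no calculation on this point. The check is therefore of the schedule, of what happens to each type of early stopper, and of the weight of one person.

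**Schedule.** Visits are at weeks 0, 12, 18, 24 and 36 (Outcomes). Therapy begins at week 12, after the wait, at 2 sessions a week for 12 weeks (Intervention).
- Visits before exposure: weeks 0 and 12, taking the week-12 assessment to precede the first session.
- First visit after exposure: week 18.
- Sessions before it: 2 × (18 − 12) = up to 12, of 2 × 12 = 24 planned.

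**Three routes for a participant who stops HELLEN between weeks 12 and 18.**
1. Lost to follow-up: the last observation is the week-12 answer, which LOCF enters at weeks 18, 24 and 36.
2. Asks to be removed: the data are destroyed. Nothing is carried forward, and no view is recorded.
3. Stops HELLEN but stays in the trial: assessed at week 18 as planned, so a post-exposure answer exists.

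Only route 1 puts a pre-exposure score at a post-exposure visit. Route 2 also loses the view, but by deletion.

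**Weight.** The planned sample is 20 (Sample Size), so each person is 1/20 = 5%. If k participants follow route 1 and none follows route 2:

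overstatement of the mean = (k/20) × D,

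where D is the average of (week-12 attitude minus true post-exposure attitude) among those k. If D is negative the bias is downward, and if D is zero there is none.

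**Illustration on assumed figures only.** Suppose 80% of the 20 − k who continue are favourable, and the k lost were all favourable beforehand and all unfavourable after use. The reported proportion is [0.8 × (20 − k) + k]/20 and the true one is 0.8 × (20 − k)/20.

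| k | Reported | True |
|---|---|---|
| 1 | 16.2/20 = 81% | 15.2/20 = 76% |
| 2 | 16.4/20 = 82% | 14.4/20 = 72% |
| 4 | 16.8/20 = 84% | 12.8/20 = 64% |

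These rows are the extreme case, a complete reversal of opinion in every person lost.

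**Chance that it arises at all.** For an assumed probability d that a participant is lost early, the chance of at least one among 20 is 1 − (1 − d)^20. This gives 64% for d = 5%, 88% for d = 10% and 99% for d = 20%. The protocol states no value for d.

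**The case against.** The strongest reply is that the plan promises less about this form than one might suppose. Acceptability appears once, in the rationale. No endpoint, threshold or analysis carries that label, and attitude is not among the types of secondary outcome named under Outcomes. A reader might infer that the plan reports the carried-forward score as its acceptability result. The protocol does not say so. What stands is that this is the only listed instrument bearing directly on acceptability, and that the LOCF rule has no exception for it.

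Repetition of the form is also inferred. The list mixes screening and demographic forms with outcome measures, and the attached form is not shown. This does not rescue the plan: if the form were given only at week 0, there would be no post-exposure attitude data from anyone.

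The affected group is narrow. A reader might infer that everyone who stops early is carried forward, but routes 2 and 3 above show otherwise. Therapy is also given as tolerated, so difficulty may lead to modification and not to exit. A reader might likewise infer that LOCF forces each such person's change to zero. That is true only relative to week 12; change from week 0 is the week-12 score minus the week-0 score.

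People may leave for reasons unrelated to the device, so the upward direction is plausible but not certain. Finally, carrying forward a pre-treatment value is a general weakness of LOCF. What is particular here is the change in what the score means once the device has been used, together with the absence of any collection at exit.

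**Conclusion.** The concern holds in a limited form. On the general schedule, a participant lost to follow-up between weeks 12 and 18 would have a pre-exposure attitude entered at weeks 18, 24 and 36, and nothing is planned that would capture that person's view after use. The bias is (k/20) × D and is upward if those lost like the device less than they had expected to. Its size cannot be fixed, because the protocol gives no scale, no expected fall and no dropout rate.

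The conclusion rests on two readings: that the form follows the general schedule, and that the week-12 assessment precedes the first session. The documents do not support saying that all early stoppers are affected, or that a biased acceptability endpoint has been specified. The point is worth acting on before data collection because the remedy is small and a missed answer cannot be recovered later.

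**What to change.** - Give the existing attitude questionnaire when a participant stops HELLEN or leaves the trial, by phone if needed.
- Optionally, give it once early in therapy to all participants. The oxygen test at the 3rd or 4th session is only for those who agree to it, but those sessions are part of everyone's therapy and could carry the form.
- Exempt this questionnaire from LOCF, so that no week-0 or week-12 score is entered at a post-exposure visit.
- Report post-exposure attitude among those who answered, with the number of exposed participants who gave no post-exposure answer and their reasons for stopping.

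The cost is one short existing form, given by existing staff, and slightly more burden for participants. Some of those lost will remain unreachable, so the gap is reduced and made visible, not closed. The attitude figure may also turn out less favourable. Treatment itself is unchanged.

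### Data of participants who ask to be removed from the study are dropped from analysis and destroyed, which conflicts with the protocol's intention-to-treat and LOCF rule

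*Protocol*

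**What the plan says.** Protocol, Data Management, in the paragraph on coding and confidentiality: subjects stay de-identified unless they ask to be taken out of the study, "in which case their data will be re-identified, removed from analysis, and destroyed". The sentence does not separate data already collected from data still to come, and it does not exempt safety data. The same section also says that all data are held for five years.

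Protocol, Data Collection Methods: "For any participants who are lost to follow-up, their last measurements will be imputed into the data and analysed according to intention to treat principles".

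Protocol, Statistics (the commitment appears in both paragraphs): "All analyses will be conducted on an intention-to-treat basis, with missing follow-up data conservatively imputed using the last observation carried forward method".

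Protocol, Sample Size: "20 participants with MS will be invited to participate in this pilot trial". The protocol gives no withdrawal rate.

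Protocol, Background and Rationale: the pilot is to supply "preliminary data required about safety, feasibility and effect size estimates" before a larger randomised trial. Objectives adds "highlighting any barriers and risks to its potential use in this population".

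Protocol, Data Monitoring and Harms: adverse events are documented and reported to the ethics committee. There is no data monitoring committee.

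**The concern.** The deletion rule is triggered by a wish to leave the study, not by a wish to have data withdrawn. These are different requests, and the protocol does not distinguish them. Who is analysed then depends on how a person leaves, and that may depend on how the person fared with the device.

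The pilot exists to inform a larger trial on safety, feasibility and effect size. If participants who leave on request had less benefit or more problems, removing them makes the mean change look larger and the event proportion look smaller. A statistical analysis plan could not repair this later, because destroyed records cannot be analysed or used in a sensitivity analysis.

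**Working it through.** **1. The rules side by side.** The protocol states no figure on this point that could be reproduced, so the check starts from the text. Take a participant whose last assessment is at week 18, with measurements at weeks 0, 12 and 18.

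- *Stops attending without a word.* Data Collection Methods applies: the week 18 value is carried forward and the person is analysed.
- *Stops or reduces therapy but stays in the study.* The Intervention section lets the researchers adjust or stop the exercise and attaches no data deletion. The person is analysed.
- *Asks to be removed from the study.* Data Management applies: all three assessments are removed and destroyed. Statistics says that all analyses are intention-to-treat with LOCF, which would keep them. Both cannot be done.

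The conflict is therefore confined to the third route.

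**2. Effect on the mean change.** Inputs: N = 20 (Sample Size). Assumed, because the protocol gives no values: w participants ask to be removed, those who stay change on average by d_s, and leavers by d_l under LOCF.

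- All kept: mean = [(N − w)·d_s + w·d_l] / N
- After deletion: mean = d_s
- Shift = (w/N)·(d_s − d_l). If d_l = 0, the inflation ratio is N/(N − w).

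With d_s = 0.50 SD and d_l = 0:

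| w | All 20 kept | After deletion | Ratio |
|---|---|---|---|
| 0 | 0.50 | 0.50 | 1.00 |
| 2 | 18 × 0.50 / 20 = 0.45 | 0.50 | 20/18 = 1.11 |
| 4 | 16 × 0.50 / 20 = 0.40 | 0.50 | 20/16 = 1.25 |
| 6 | 14 × 0.50 / 20 = 0.35 | 0.50 | 20/14 = 1.43 |

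Zero change is what LOCF itself gives, measured from week 12, for anyone who leaves between the week 12 and week 18 assessments. For later leavers it is only an assumption. With w = 4 and d_l = 0.25 SD, the mean over all 20 is (16 × 0.50 + 4 × 0.25)/20 = 0.45 SD and the ratio is 0.50/0.45 = 1.11. If leavers changed as much as the others (d_l = d_s), the shift is zero. If they changed more, deletion works against the device.

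**3. Effect on event proportions in the study dataset** (all event patterns assumed).

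- Every leaver had an event and nobody else did: for w = 2, 4, 6 the proportion is 2/20 = 10%, 4/20 = 20%, 6/20 = 30% with all kept, against 0/18, 0/16, 0/14 after deletion.
- Four leave, three of them after an event, none among the rest: 3/20 = 15% (exact 95% CI 3–38%) against 0/16 = 0% (0–21%).
- Four leave without events, two events among the rest: 2/20 = 10% against 2/16 = 12.5%. Here the shift goes against the device.

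**4. Loss of information alone.** With no events seen, the one-sided 95% upper bound is 1 − 0.05^(1/n): 13.9% for n = 20 and 17.1% for n = 16. The chance of seeing at least one event with a true risk of 10% is 1 − 0.9^n: 87.8% for n = 20 and 81.5% for n = 16. This cost is modest. Selective removal matters more.

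**The case against.** The strongest reply is that the rule is narrow. It stands in a confidentiality paragraph and explains when the code may be broken, so it can be read as covering only a participant who asks for the record to be taken out. Honouring such a request is legitimate. The information statement and consent form are not shown and may already separate leaving the study from withdrawing data. This is also a single-arm pilot of 20, with no randomised comparison for intention-to-treat to protect, and the number affected may be zero.

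Much of this stands. A reader might infer that anyone who withdraws, or who stops because the device was not tolerated, disappears from the trial. The documents do not support that: participants lost to follow-up are kept by LOCF, and stopping therapy carries no deletion. A reader might also infer that harms are erased. Adverse events already reported to the ethics committee remain on record there. Nor does anything say that counts of those enrolled or withdrawn are destroyed, so deletion need not turn 16 of 20 completers into 16 of 16.

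Three things remain. As worded, the trigger is the wish to leave the study, and if only data-withdrawal requests were meant, the text does not say so. No exception is made for safety data. Selection related to outcome biases a pre-post mean with or without randomisation: the comparison stays within person, but describes only those who remained.

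**Conclusion.** The contradiction is real and can be read directly from the text: for a participant who asks to be removed, the deletion rule and the intention-to-treat/LOCF rule cannot both be followed. Its scope is that group only.

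The direction of bias is an inference. It favours the device if those who ask to leave did worse or had device-related problems, which is plausible but is not stated in the protocol. The size cannot be known from the document. It runs from nil (no requests, or leavers like the others) to an inflation of the mean change by 11%, 25% or 43% for 2, 4 or 6 requests among 20, on the assumption of zero change in leavers and 0.50 SD in the others. The event proportions in the working are constructed cases, not forecasts.

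This should be fixed before data are lost, because destruction is irreversible and bears on the estimates that the pilot is meant to deliver. Because the group is limited and may be empty, it is a should-fix and does not invalidate the design.

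**What to change.** Amend Data Management to say that a request to leave the study ends further sessions and visits, while data collected up to that point are kept and analysed under the intention-to-treat rule in Statistics. Delete outcome data only on a separate, explicit request to withdraw data. Even then, keep a non-identifiable count of the withdrawal, its reason and any adverse event, so that participant flow and safety denominators still refer to everyone enrolled. Check that the information statement and consent form agree with the amended rule, and that it fits the ethics approval and the five-year retention statement.

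The cost is a minor amendment, with no extra participants or visits. Participants keep the right to have their data deleted, so a few outcome records may still be lost.
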